6.1 Recruitment

A flow diagram (as recommended by CONSORT) will be produced to describe the participant flow through each stage of the trial. The consort diagram will include the reasons for the loss of primary outcome data (Drop-outs and withdrawals) over the course of the trial.

6.2 Baseline Characteristics

Categorical data will be summarised by frequencies and percentages. Continuous data will be summarised by the number of responses, mean and standard deviation if deemed to be normally distributed, and the number of responses, median and interquartile range or total range if data appear skewed. Tests of statistical significance will not be undertaken, nor confidence intervals presented ⁷.

7. Statistical Analysis

7.1 Primary outcome:

The primary outcome is the incidence of postoperative delirium during 7 postoperative days, diagnosed with the Confusion Assessment Method, and will be a categorical variable.

7.2 Secondary outcome measures are as follows:

- The subtype, severity, and duration of delirium in 7 days after the surgery, diagnosed with the Delirium Rating Scale-Revised-98 and confusion Assessment Method, subtypes and duration of delirium are categorical variables, and severity score is a continuous variable;
- Duration of delirium, measured by days from the onset of delirium symptom to the resolution of symptoms, which is a continuous variable;
- The intensity of postoperative pain, measured with acute pain score in 7 days after the surgery using Visual Analogue Scale (VAS), which is a continuous variable;
- The occurrence of non-delirium in-hospital complications within 30 days after surgery, including chest infection, myocardial infarction, renal failure, gastrointestinal ileus, which is a categorical variable;
- Length of hospital stay, measured by the sum of inpatient days from admission to discharge, which is a continuous variable;
- Mortality during the hospital stay and during the follow-up period after hospital admission, which is a categorical variable;
- Incidence of delirium in the clinic or at the residence on 30-day, 6 months, 12 months after surgery, diagnosed with CAM, which is a categorical variable;
- Cognitive and functional decline on 30-day, 6 months, 12 months after surgery, diagnosed with Mini-Mental State Examination (MMSE) and Hospital Anxiety and Depression Scale, which is a categorical variable;
- Quality of life on 30 days, 6 months, 12 months after surgery, using 36-Item Short Form questionnaire, which is a categorical variable;

- Economic parameters, including total cost in hospital and expenditure for anesthesia and resource using costs, including equipment and disposables required for each anesthetic technique, which are the continuous variables.

8. Analysis Methods

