The incidence of delirium before surgery includes (delirium from admission to surgery). CAM scale is used for the diagnosis of delirium in the ward; the CAM-ICU scale is used to diagnose delirium in the intensive care unit, that is, CAM-ICU is used when the CAM is not available. When there is a contradiction between the diagnosis obtained by the scale and the psychiatrist's diagnosis, when there are still differences after consultation, the diagnosis of the psychiatrist shall prevail. To prevent missed diagnosis, we should communicate with the medical staff in the ward on time. After the patient is selected, the family member or escort staff should be informed. The researcher should be informed of the evaluation of delirium when any abnormal performance of the patient's mood, consciousness, cognition and so on is found. When postoperative delirium is found, the subject should communicate with the competent physician and decide on further diagnosis and treatment if the patient's performance was normal 7 d after the operation, the visit ended, while the patient with continuous delirium was followed up until normal or discharged. Delirium patients were assessed by delirium rating scale 98 revised (DRS-R-98) for type and severity of delirium. The patient's assessment form was used as evidence of postoperative delirium and the duration of delirium.

10. Data collection

Arrange post-operative delirium assessment and data collection by a fixed staff member who should not know about the study design and purpose to reduce the error in the study report, assess the presence, type, severity of postoperative delirium daily, patient medical records and nurse records are also used to determine whether delirium occurs for a total of 7 days after surgery (delirium was observed and discharged). The data collection table is shown in Table 1. Besides, the mortality, hospitalization time, and discharge department were recorded. Table 2 summarizes other data to be collected.

Table 1 Data collected daily. P: days after surgery

| Time points | Preoperative evaluation | P1 | P2 | P3 | P4 | P5 | P6 | P7 |
|---|-------------------------|----|----|----|----|----|----|----|
| Temperature | * | * | * | * | * | * | * | * |
| Blood pressure | * | * | * | * | * | * | * | * |
| Heart rate | * | * | * | * | * | * | * | * |
| Oxygen saturation | * | * | * | * | * | * | * | * |
| Hemoglobin | * | * | * | * | * | * | * | * |
| Alanine aminotransferase | * | * | * | * | * | * | * | * |

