2.2 Objectives

This clinical trial is pragmatic, multicentre, prospective, parallel grouped, randomised controlled. The RAGA trial aims to determine whether different types of anaesthesia (regional anaesthesia vs general anaesthesia) given to older patients undergoing hip fracture surgery result in the equivalent incidence of postoperative delirium.

This will be met through meeting the following aims (as specified in the protocol):

- Aim 1: To assess whether there are differences in the incidence of postoperative delirium in different groups (by age, existing cognitive impairment, or preoperative delirium) between groups;

- Aim 2: To compare the subtypes, severity, and duration of postoperative delirium between the anaesthesia groups;
- Aim3: To describe the pain scores in the postoperative period either regional anaesthesia or general anaesthesia;
- Aim4: To compare the occurrence of non-delirium complications between the groups;
- Aim 5: Assessment of the length of hospital stay between groups;
- Aim 6: Assessment of the mortality during the hospital stay and the follow-up period after hospital admission between groups;
- Aim 7: Assessment of the cognitive and functional decline and quality of life on 30 days, 6 months, and 12 months after surgery between groups.
- Aim 8: To assess the cost-effectiveness of using regional anaesthesia compared to general anaesthesia in terms of total in-hospital costs and expenditure of anaesthesia.

3. Study Methods

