3.2 Randomisation

Randomisation to regional anaesthesia or general anaesthesia is conducted in a 1:1 ratio, one day before surgery, using computer-generated assignment (web or telephone developed by the study data management provider).

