5.2 Secondary outcomes

Severity and Subtypes

The 13 items from Delirium Rating Scale-Revised-98 contribute to a severity score (items are scored zero to three, range from zero [no delirium] to 39 [maximum severity]) including two items which also define hyperactive (score ≥ 1 on motor agitation), hypoactive (score ≥ 1 on motor retardation), mixed motor (score ≥ 1 on both motor items) or no motor (score=0 on both motor items) subtypes of delirium.

Visual analogue scale (VAS)

Pain scores are measured using VAS (ranges from 0 [no pain] to 100 [worst pain], assessed daily, over the seven days and the highest pain score will be reported as continuous data. The first three days' VAS also will be analysed by comparison between groups.

30-day mortality is all-cause mortality during 30 days post-surgery.

Length of hospital stay is calculated from the first post-operative day to discharge.

Costs of the anaesthetic procedure include the expenditure of anaesthesia; anaesthetic drug, and labour cost.

Total in-hospital costs include the expenditure of anaesthesia, surgery, and hospitalisation.

5.3 Subgroups:

Pre-delirium is defined as whether patients had delirium before the intervention, using the Confusion Assessment Method on the day of admission.

Pre-existing dementia is defined by the Mini-Mental State Examination (MMSE) score with thresholds adjusted for educational levels.

- MMSE scores from 0 to 17 without educational experience/illiteracy;
- MMSE scores from 18 to 20 with an educational level less than primary education;
- MMSE scores from 21 to 22 with an educational level less than high school diploma;
- MMSE scores from 23 to 24 with an educational level less than a bachelor's degree.

Age is categorised by groups 65 to 80 years vs >80 years.

6. Trial Population

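### SAP 7.2 defines delirium duration in two unreconciled ways, and one of them, read literally, can count days before anaesthesia

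*SAP*

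**What the plan says.** SAP 2.2, Aim 2, sets the objective: "To compare the subtypes, severity, and duration of postoperative delirium between the anaesthesia groups".

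SAP 7.2 then lists duration twice, in consecutive bullets.

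- First bullet: "The subtype, severity, and duration of delirium in 7 days after the surgery, diagnosed with the Delirium Rating Scale-Revised-98" and the Confusion Assessment Method (CAM), adding that "subtypes and duration of delirium are categorical variables, and severity score is a continuous variable".
- Second bullet: "Duration of delirium, measured by days from the onset of delirium symptom to the resolution of symptoms, which is a continuous variable".

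SAP 5.2, which defines the derived secondary variables, has no entry for duration. SAP 8.2 (SO2) analyses duration with descriptive statistics and a generalised linear model (GLM), and names no covariate.

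Preoperative delirium is not an exclusion in protocol 5.3. It is a planned subgroup in SAP 5.3: "Pre-delirium is defined as whether patients had delirium before the intervention, using the Confusion Assessment Method on the day of admission". Protocol section 9 (Description) uses a wider window: "The incidence of delirium before surgery includes (delirium from admission to surgery". Randomisation takes place "one day before surgery" (SAP 3.2).

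**The concern.** Aim 2 concerns postoperative delirium. Some patients will already be delirious when they are randomised or anaesthetised, and the second bullet has no rule for them. Its clock starts when symptoms start, whenever that was. It would even give a positive duration to a patient who was delirious at admission and clear before surgery.

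Two things are at stake. First, analysts following different bullets would build different SO2 datasets, and the choice could be made after the data are seen. Second, under the second bullet SO2 would mix preoperative illness and waiting time with whatever the anaesthetic does. That blurs the comparison and lets a chance imbalance in preoperative delirium feed directly into the estimate.

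**Working it through.** **The two rules side by side**

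| | First bullet, SAP 7.2 | Second bullet, SAP 7.2 |
|---|---|---|
| Start | After surgery | Symptom onset, no lower limit |
| End | Day 7 | Resolution, no upper limit |
| Scale | Categorical | Continuous |
| Likely analysis in SAP 8.2 | SO1: counts and relative risk | SO2: GLM |

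The last row is an inference. SO1 to SO5 follow the order of the bullets in 7.2, so SO2 appears to belong to the second bullet.

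**Does any other text settle the start?**

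- Protocol section 9 takes duration from the patient's assessment form and gives no start date.
- Protocol Table 1 has one preoperative column, then daily assessment on P1 to P7.
- Protocol section 9 follows persistent delirium past day 7, until the patient is normal or discharged. The 7-day limit is therefore not applied throughout.
- SAP section 9 limits the preoperative-delirium subgroup analysis to the primary outcome, so it does not cover duration.

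None of these fixes a start for delirium already present at surgery.

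**What the second rule can count.** Take a hypothetical patient who is CAM-positive at admission, has surgery 5 days later and is clear on P3: about 5 + 3 = 8 days. A patient with onset on P1 who is clear on P3 has about 3 − 1 = 2 days. With randomisation one day before surgery, about four of the first patient's five preoperative days also precede randomisation. Delirium that begins between randomisation and surgery precedes anaesthesia only.

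**Illustration of size.** The documents state no figure for duration, so there is none to reproduce. The 441 per group in SAP 3.3 concerns the primary outcome and is unaffected. Every input below is an assumption:

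- D: mean postoperative duration in delirious general-anaesthesia (GA) patients, 2 or 3 days.
- r: true regional (RA) to GA ratio of postoperative duration, 0.70.
- q: share of delirious patients with preoperative onset, 0.1 to 0.5, equal in both arms.
- m: mean preoperative delirium days in those patients, 1 to 5.
- Exponential-like spread, with pre- and postoperative days independent.

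Formulas:

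- GA mean = D + qm; RA mean = rD + qm.
- Difference = (1 − r)D, which does not contain q or m.
- Variance added by preoperative days = 2qm² − (qm)².
- SD factor in GA = √(D² + added variance) / D.

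For D = 2, q = 0.3, m = 3:

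- GA mean = 2 + 0.9 = 2.9; RA mean = 1.4 + 0.9 = 2.3.
- Difference = 0.6; ratio = 2.3/2.9 = 0.79.
- Added variance = 5.4 − 0.81 = 4.59; SD factor = √8.59 / 2 = 1.47.

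| D | q | m | GA mean | RA mean | Difference | Ratio | SD factor |
|---|---|---|---|---|---|---|---|
| 3 | 0.1 | 1 | 3.1 | 2.2 | 0.9 | 0.71 | 1.01 |
| 3 | 0.3 | 3 | 3.9 | 3.0 | 0.9 | 0.77 | 1.23 |
| 2 | 0.3 | 3 | 2.9 | 2.3 | 0.6 | 0.79 | 1.47 |
| 2 | 0.5 | 5 | 4.5 | 3.9 | 0.6 | 0.87 | 2.38 |

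The first and last rows are the extremes of the grid. The expected difference in days is unchanged, the ratio moves towards 1, and the spread grows.

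**The case against.** The best defence is that the second bullet only says how the duration named in the first is measured. On that reading the postoperative window carries over, Aim 2 confirms it, and a schedule with daily assessment only on P1 to P7 fits it. This stands far enough to rule out saying that SO2 will include preoperative days. It does not resolve the conflict: the bullets still differ on scale, and neither says what to do with delirium already present at surgery.

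Three stronger inferences are tempting, and the documents do not support them.

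- A reader might infer from the single preoperative column in Table 1 that onset dates would rest on recall. No text says so, and SAP 5.3 has a CAM on the day of admission.
- A reader might take the 3-week limit in protocol 5.1 as a guide to the length of preoperative delirium. It limits the age of the fracture.
- A reader might infer bias towards one arm. Randomisation balances preoperative days in expectation.

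It is also fair that duration is a secondary outcome, and that SAP 4.3 makes no multiplicity correction and warns against inferring treatment effects from the intervals. That limits the stakes, but it is no reason to leave the endpoint with two definitions.

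**Conclusion.** The point holds as a conflict between two stated definitions. One is postoperative, limited to 7 days and categorical; the other is open at both ends and continuous. Followed literally, the second departs from Aim 2, because it can count days that precede anaesthesia and often randomisation.

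The harm is noise and dilution of a ratio, plus exposure to chance imbalance. Its size in this trial cannot be computed from the documents. The illustrated ranges (ratio 0.71 to 0.87 instead of 0.70, SD factor 1.01 to 2.38) depend wholly on the assumed inputs.

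The absence of systematic bias follows from randomisation for all randomised patients. If SO2 is restricted to delirious patients, on which the SAP is silent, it also needs the share with preoperative onset to be similar in the two arms, as the illustration assumes. The primary outcome and its sample size are not affected.

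**What to change.** In SAP 7.2, replace both definitions with one: the number of CAM-positive days counted from the first postoperative assessment over P1 to P7. Days before surgery are never counted. Remove duration from the categorical bullet and analyse it in SO2 as a continuous or count variable. Say whether patients with no CAM-positive day contribute a zero. Report the protocol's follow-up until normal or discharge separately.

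In SAP 8.2, add preoperative delirium, from the admission CAM as defined in SAP 5.3, to the SO2 GLM as a baseline covariate. Moving the clock alone would not suffice: if patients already delirious also stay delirious longer after surgery, a chance imbalance would still reach the estimate.

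The cost is a short edit in two SAP sections, with no new data, since the admission and daily CAM records are already planned. The main downside is that duration beyond day 7 is truncated in the main SO2 analysis. A smaller one is that an admission CAM misses delirium starting later but before surgery, so the covariate removes only part of the imbalance.

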3.3 Power and Sample Size

Based on the previously published incidence of postoperative delirium diagnosed using Confusion Assessment Method ranged from 28% to 50% in the elderly patients (age 65) during the hospital stay for hip fracture surgery, the observational studies in China estimated 3-day postoperative delirium incidences of 11.1%–23.3%.⁴⁻⁶ Assuming postoperative delirium incidences in general anaesthesia OF 26% and a reduction of 30% postoperative delirium in RA, 441 patients should be needed for each group to give power (1- β) of 80% and the significance level of 5% (two-sided). With an estimated drop-out rate of 10%, a total of 1000 patients will be recruited from the nine clinical trial centers in China.

4. Statistical Principles

Statistical analysis will be conducted in accordance with the plan outlined in the SAP. Statistical analysis will abide by these general statistical principles below.

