8.2 Secondary outcomes (SO)

SO1: Frequency counts will be summarised by treatment group. RR and associated 95% CI will be calculated.

SO2: Duration of delirium will be summarised using basic descriptive statistics and analysed using generalised linear model (GLM) methods.

SO3: Acute pain score using VAS will be summarised using basic descriptive statistics and analysed using GLM methods.

SO4: Occurrence of non-delirium in-hospital complications within 30 days after surgery will be summarised by treatment group, but no relative effect will be calculated.

SO5: Length of hospital stay will be summarised using median and IQR and analysed using GLM methods.

9. Planned subgroup analyses

Interpretation of subgroup analysis will be treated with caution (output will be treated as exploratory rather than definitive⁸). Analysis will be limited to the primary outcome, which is the incidence of postoperative delirium during 7 postoperative days, and the following subgroups

- Age, as defined by 65-80, >80
- Preoperative dementia, those with vs those without
- Preoperative delirium, those with vs those without.

The effects of these subgroups will be examined by adding the subgroup by treatment group interaction parameters to the log-binomial model. Wald tests will determine statistical significance (p-values) of these interaction parameters. Differences between the treatment groups within subgroups will only be examined if the interaction parameter is shown to statistically important (p-value <0.05).

10. Definitions and Derived Variables

Abbreviations & Definitions	
Abbreviation/acronym	Meaning
BCTU	Birmingham Clinical Trials Unit
BP	Blood Pressure
CONSORT	Consolidated Standards of Reporting Trials
DMC	Data Monitoring
ITT	Intention to Treat
SAE	Serious Adverse Event
SAP	Statistical Analysis Plan
TSC	Trial Steering
POD	Postoperative Delirium
GA	General Anesthesia
RA	Regional Anesthesia
GLM	Generalised Linear Model
Term	Definition
International Standard Randomized Controlled Trial	A Clinical Trial Registry
Protocol	Document s details the rationale, objectives, design, methodology, and statistical considerations of the study
Randomisation	The process of assigning trial subjects to Intervention or control groups using an element of chance to determine the assignments in order to reduce bias.
Statistical Analysis Plan	Pre-specified statistical methodology documented for the trial, either at the protocol or in a separate document.

11. Software Details

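### SAP 7.2 types delirium duration two ways and defines it so that SO2, run as written, compares only delirious patients; severity has no settled population and no named model

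*SAP*

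**What the plan says.** **Duration.** Aim 2 in SAP 2.2 is a between-group comparison of subtype, severity and duration. In SAP 7.2 the first bullet sets a 7-day window and states that "subtypes and duration of delirium are categorical variables". The next bullet reads "Duration of delirium, measured by days from the onset of delirium symptom to the resolution of symptoms, which is a continuous variable" and gives no window. In SAP 8.2, SO2 analyses duration by generalised linear model (GLM) and states no population, distribution, link, or rule for unresolved delirium or death. Under the protocol (section 9, Description), "the patient with continuous delirium was followed up until normal or discharged".

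**Severity.** The same protocol text says "Delirium patients were assessed by delirium rating scale 98 revised (DRS-R-98) for type and severity of delirium". Protocol Table 1, however, marks DRS-R-98 before surgery and on each of days P1 to P7, without restriction, and protocol section 10 has staff rate severity daily. SAP 5.2 gives the score a zero, labelled as no delirium. SAP 7.2 calls the score continuous. SAP 8.2 names no model for it.

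**Population.** SAP 4.6 puts all secondary outcomes on an intention-to-treat basis with every participant included.

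**The concern.** An interval from onset to resolution does not exist for a patient with no onset, and the SAP nowhere assigns such patients zero days. A GLM fitted to the variable as defined therefore drops them and keeps only patients who had the primary-outcome event. The trial is designed on the expectation that anaesthesia changes how many patients have that event, so randomisation no longer protects the comparison. If the cases that RA prevents are the short ones, the RA cases that remain are longer on average even when RA lengthens nobody's delirium.

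The end of the interval is also open. A patient discharged while delirious has no resolution date. Protocol section 1 cites a systematic review of 18 prospective studies in which delirium persisted at discharge in 44.7%, so the situation is foreseeable.

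With two variable types for duration, no settled population for severity and no model for the score, the choices could be made after the data are seen. SAP 4.3 presents every comparison as hypothesis-driven and applies no multiplicity correction.

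**Working it through.** **1. The plan's own figure.** SAP 3.3: "Assuming postoperative delirium incidences in general anaesthesia OF 26% and a reduction of 30% postoperative delirium in RA", with 80% power and two-sided 5% significance.
- RA incidence: 0.26 × 0.70 = 0.182.
- Unpooled normal approximation: n = (1.960 + 0.842)² × (0.26 × 0.74 + 0.182 × 0.818) / 0.078² = 441 per group after rounding up.
- The stated 441 reproduces (the pooled form gives 444). No design figure is given for duration or severity.

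**2. Size of the delirious subset.** SAP 3.3: "With an estimated drop-out rate of 10%, a total of 1000 patients will be recruited".
- Evaluable: 1000 × 0.90 = 900, or 450 per arm.
- GA: 450 × 0.26 = 117. RA: 450 × 0.182 = 81.9, about 82.
- Together about 199 of 900 (22%). The arms differ by about 35 patients, the cases the design expects RA to prevent.

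**3. What selection can do.** The durations are assumptions, not figures from the documents. Let 18.2% become delirious under either anaesthetic, with mean 3 days that anaesthesia does not change. Let the 7.8% who become delirious only under GA have mean *m* days.
- Delirious only: GA mean = (0.182 × 3 + 0.078 × *m*) / 0.26 = 2.1 + 0.3*m*; RA mean = 3.
- All patients, zero if no delirium: GA mean = 0.546 + 0.078*m*; RA mean = 0.182 × 3 = 0.546.

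| *m* (days) | GA, delirious only | RA, delirious only | RA − GA, delirious only | RA − GA, all patients |
|---|---|---|---|---|
| 1 | 2.4 | 3.0 | +0.6 | −0.08 |
| 2 | 2.7 | 3.0 | +0.3 | −0.16 |
| 3 | 3.0 | 3.0 | 0 | −0.23 |

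RA helps in every row. The delirious-only comparison shows it as worse in two rows and as no different in the third.

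**4. What stopping at discharge can do.** Assume exponential durations with means of 4 and 3 days (true ratio 0.75) and recording that stops *c* days after onset in both arms. The observed mean is μ(1 − exp(−*c*/μ)).
- *c* = 3: 1.90 / 2.11 = 0.90
- *c* = 5: 2.43 / 2.85 = 0.85
- *c* = 7: 2.71 / 3.30 = 0.82
- *c* = 10: 2.89 / 3.67 = 0.79

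Taking discharge as the end date therefore pulls the ratio towards 1. Dropping patients without an end date would be a different choice, and the SAP does not say which applies.

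**5. Severity, passages side by side.** The sentence in protocol section 9 points to delirious patients. Table 1, protocol section 10, the zero in SAP 5.2 and the all-participants rule in SAP 4.6 point to everyone. They cannot all be followed.

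**The case against.** The strongest reply is that the documents never say Aim 2 is restricted to delirious patients. A reader might infer that duration and severity can be defined only in such patients; that goes too far. Severity has an explicit zero, Table 1 schedules the scale daily for all, and SAP 4.6 includes all participants. Zero days could also be assigned for duration. This stands for severity, where the fault is inconsistency. For duration it stands only in part: zero could be assigned, but the SAP does not do so, and SAP 4.6 cannot be carried out for SO2 until it does.

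Two other inferences are not supported:
- **Severity cut off at discharge.** Its window in SAP 7.2 is 7 days, so discharge matters only if it comes before day 7.
- **Severity assigned counts and a relative risk.** The entry "SO1: Frequency counts will be summarised by treatment group" names no outcome, and any link to severity rests on list order, with ten bullets in 7.2 against five SO entries in 8.2. What can be said is that no model for the score is named.

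It is also fair to say that incidence is the primary outcome and would be reported alongside, so fewer RA cases would be visible, and that SAP 4.3 warns against inferring treatment effects from the intervals. Both points soften the consequence but leave the estimate undefined. Finally, delirium days in all patients combine incidence with duration, which question 1 of protocol section 1 lists separately. That is a real cost of the remedy and a reason to keep the delirious-only summaries as description.

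**Conclusion.** The point holds for duration as defined and, in a weaker form, for severity. The contradictory typing, the missing rules for unresolved delirium and death, and the absence of a severity model are plain from the text. That SO2 would compare about 117 with 82 patients follows from the written definition and the planned rates of 26% and 18.2% at 450 per arm.

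A reader might conclude that the plan will report a benefit of RA as harm. The documents do not support that. The reversal rests on assumed durations, shrinks as prevented cases lengthen, and is zero when they last as long as the others. Even then the delirious-only result hides the benefit. The supportable statement is that such a comparison can hide or reverse a benefit: +0.6 to 0 days among delirious patients against −0.08 to −0.23 days among all, under the stated assumptions.

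The primary analysis and the sample size are unaffected.

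**What to change.** - **Typing.** Delete duration from the categorical list in SAP 7.2.
- **Duration.** For the between-group comparison, use the number of CAM- or CAM-ICU-positive days in postoperative days 1-7 for all patients in the analysis set, zero if none, analysed by a negative binomial or quasi-Poisson GLM. State how this set relates to the Full Analysis Set in SAP 4.4.2, which requires at least one efficacy assessment.
- **Early discharge and death.** State how days after death or discharge before day 7 are handled, for example by an offset for days assessed. Because an offset treats unassessed days as like assessed ones, add a sensitivity analysis under another stated assumption.
- **Severity.** Analyse peak observed DRS-R-98 severity over days 1-7 as a continuous score in all patients, with a named model. Use recorded scores wherever they exist, and enter 0 only where no score was taken because CAM was negative. Reconcile the protocol section 9 sentence with Table 1.
- **Delirious-only results.** Keep duration and severity among delirious patients as descriptive summaries.

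The cost is SAP wording plus one protocol clarification, since daily CAM is already scheduled. The drawbacks are many zeros, a measure that combines incidence with duration, and delirium beyond day 7 that is only described.
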